Change from Baseline IIQ Total Score at 12 Months	Continuous	The Incontinence Impact Questionnaire-Total Score will be computed at baseline and 12 months (and 3 and 6 months) using the standard scoring algorithm. Specifically, instructions are to sum the Physical Activity, Travel, Social Relationships, and Emotional Health subscale scores of the IIQ. If any subscale scores are missing, then no Total score will be calculated. The outcome will then be computed as the difference in Total score at 12 months (and 3 and 6 months) and the Total score at baseline. If data for an assessment time point are missing, the outcome variable will be coded as missing.
Change from Baseline EQ-5D Total Score at 12 Months	Continuous	The EQ-5D Total Score will be computed at baseline and 12 months (and 3 and 6 months) using the algorithm obtained from https://archive.ahrq.gov/professionals/clinicians-providers/resources/rice/EQ5Dscore.html . The outcome will then be computed as the difference in Total score at 12 months (and 3 and 6 months) and the Total score at baseline. If data for an assessment time point are missing, the outcome variable will be coded as missing.
Change from Baseline EQ-5D Visual Analogue Scale (VAS) at 12 Months	Continuous	The EQ-5D VAS is the response to a single question from the EQ-5D. The outcome will then be computed as the difference in EQ-5D VAS at 12 months (and 3 and 6 months) and the EQ-5D VAS at baseline. If data for the assessment time point are missing, the outcome variable will be coded as missing.
Change from Baseline PISQ-IR not sexually active – partner related subscale score at 12 months	Continuous	The PISQ-IR not sexually active – partner related subscale score will be computed at baseline and 12 months (and 3 and 6 months) using standard scoring algorithms. Specifically, instructions are to sum the scores for questions Q2a, Q2b (1=strongly agree, ..., 4=strongly disagree). If there is more than 1 missing response then a total score is not calculated. To handle missing values, the final score is obtained by dividing the sum by the number of items answered. The outcome will then be computed as the difference in score at 12 months (and 3 and 6 months) and the score at baseline. If data for an assessment time point are missing, the outcome variable will be coded as missing. Scores should only be calculated for participants that are not sexually active.

Network

Protocol ESTEEM Statistical Analysis Plan

Variable	Type	Definition
Change from Baseline PISQ-IR not sexually active – condition specific subscale score at 12 months	Continuous	The PISQ-IR not sexually active – condition specific subscale score will be computed at baseline and 12 months (and 3 and 6 months) using standard scoring algorithms. Specifically, instructions are to sum the scores for questions Q2c, Q2d, Q2e (1=strongly agree, ..., 4=strongly disagree). If there is more than 1 missing response then a total score is not calculated. To handle missing values, the final score is obtained by dividing the sum by the number of items answered. The outcome will then be computed as the difference in score at 12 months (and 3 and 6 months) and the score at baseline. If data for an assessment time point are missing, the outcome variable will be coded as missing. Scores should only be calculated for participants that are not sexually active.
Change from Baseline PISQ-IR not sexually active – global quality subscale score at 12 months	Continuous	The PISQ-IR not sexually active – global quality subscale score will be computed at baseline and 12 months (and 3 and 6 months) using standard scoring algorithms. Specifically, instructions are to sum the scores for questions Q4a, Q4b, Q5a, and Q6 using reverse scores for all but Q5a (Q4a and Q4b are Likert scales of 1 to 5; Q5a: 1=strongly agree, ..., 4=strongly disagree; Q6: 1=not at all, ..., 4=a lot). If there are more than 2 missing responses then a total score is not calculated. To handle missing values, the final score is obtained by dividing the sum by the number of items answered. The outcome will then be computed as the difference in score at 12 months (and 3 and 6 months) and the score at baseline. If data at an assessment time point are missing, the outcome variable will be coded as missing. Scores should only be calculated for participants that are not sexually active.
Change from Baseline PISQ-IR not sexually active – condition impact subscale score 12 months	Continuous	The PISQ-IR not sexually active – condition subscale score will be computed at baseline and 12 months (and 3 and 6 months) using standard scoring algorithms. Specifically, instructions are to sum the scores for questions Q3, Q5b, Q5c using reverse scores for Q3 (Q3: 1=not at all, ..., 4=a lot; Q5b, Q5c: 1=strongly agree, ..., 4=strongly disagree). If there is more than 1 missing response then a total score is not calculated. To handle missing values, the final score is obtained by dividing the sum by the number of items answered. The outcome will then be computed as the difference in score at 12 months (and 3 and 6 months) and the score at baseline. If data at an assessment time point are missing, the outcome variable will be coded as missing. Scores should only be calculated for participants that are not sexually active.

Network

Protocol ESTEEM Statistical Analysis Plan

Variable	Type	Definition
Change from Baseline PISQ-IR sexually active – arousal, orgasm subscale score change from baseline at 12 months	Continuous	The PISQ-IR sexually active – arousal, orgasm subscale score will be computed at baseline and 12 months (and 3 and 6 months) using standard scoring algorithms. Specifically, instructions are to sum the scores for questions Q7, Q8a, Q10, and Q11 using reverse scores for Q11 (Q7, Q8a, Q11: 1=never, ..., 5=[almost] always; Q10: 1=much less intense, ..., 5=much more intense; check box response to Q1=1). If there are more than 2 missing responses then a total score is not calculated. To handle missing values, the final score is obtained by dividing the sum by the number of items answered. The outcome will then be computed as the difference in score at 12 months (and 3 and 6 months) and the score at baseline. If data at an assessment time point are missing, the outcome variable will be coded as missing. Scores should only be calculated for participants that are sexually active.
Change from Baseline PISQ-IR sexually active – condition specific subscale score at 12 months	Continuous	The PISQ-IR sexually active – condition specific subscale score will be computed at baseline and 12 months (and 3 and 6 months) using standard scoring algorithms. Specifically, instructions are to sum the scores for questions Q8b, Q8c, Q9 using reverse scores for all (Q8b, Q8c, Q9: 1=never, ..., 5=[almost] always). If there is more than 1 missing response then a total score is not calculated. To handle missing values, the final score is obtained by dividing the sum by the number of items answered. The outcome will then be computed as the difference in score at 12 months (and 3 and 6 months) and the score at baseline. If data at an assessment time point are missing, the outcome variable will be coded as missing. Scores should only be calculated for participants that are sexually active.
Change from Baseline PISQ-IR sexually active – partner related subscale score at 12 months	Continuous	The PISQ-IR sexually active – partner related subscale score will be computed at baseline and 12 months (and 3 and 6 months) using standard scoring algorithms. Specifically, instructions are to sum the scores for questions Q13, Q14a, Q14b using reverse scores for Q14a and Q14b (Q13: 1=all of the time, ..., 4=hardly ever/rarely; Q14a, Q14b: 1=very positive, ..., 4=very negative). If there is more than 1 missing response then a total score is not calculated. To handle missing values, the final score is obtained by dividing the sum by the number of items answered. The outcome will then be computed as the difference in score at 12 months (and 3 and 6 months) and the score at baseline. If data at an assessment time point are missing, the outcome variable will be

Network

Protocol ESTEEM Statistical Analysis Plan

Variable	Type	Definition
		coded as missing. Scores should only be calculated for participants that are sexually active and have a sexual partner.
Change from Baseline PISQ-IR sexually active – desire subscale score at 12 months	Continuous	The PISQ-IR sexually active – desire subscale score will be computed at baseline and 12 months (and 3 and 6 months) using standard scoring algorithms. Specifically, instructions are to sum the scores for questions Q15, Q16, Q17 using reverse scores for Q16 and Q17 (Q15: 1=never, ..., 5=always; Q16: 1=daily, ...,5=never; Q17: 1=very high, ..., 5=very low or none at all). If there is more than 1 missing response then a total score is not calculated. To handle missing values, the final score is obtained by dividing the sum by the number of items answered. The outcome will then be computed as the difference in score at 12 months (and 3 and 6 months) and the score at baseline. If data at an assessment time point are missing, the outcome variable will be coded as missing. Scores should only be calculated for participants that are sexually active.
Change from Baseline PISQ-IR sexually active – condition impact subscale score at 12 months	Continuous	The PISQ-IR sexually active – condition impact subscale score will be computed at baseline and 12 months (and 3 and 6 months) using standard scoring algorithms. Specifically, instructions are to sum the scores for questions Q18, Q20b-d using reverse scores for Q18 (Q18: 1=not at all, ..., 4=a lot; Q20b-d: 1=strongly agree, ..., 4=strongly disagree). If there are more than 2 missing responses then a total score is not calculated. To handle missing values, the final score is obtained by dividing the sum by the number of items answered. The outcome will then be computed as the difference in score at 12 months (and 3 and 6 months) and the score at baseline. If data at an assessment time point are missing, the outcome variable will be coded as missing. Scores should only be calculated for participants that are sexually active.
Change from Baseline PISQ-IR sexually active – global quality rating subscale score at 12 months	Continuous	The PISQ-IR sexually active – global quality rating subscale score will be computed at baseline and 12 months (and 3 and 6 months) using standard scoring algorithms. Specifically, instructions are to sum the scores for questions Q19a-Q19c, Q20a using reverse scores for Q19a-Q19c (Q19a-c: 1=satisfied, ..., 5=dissatisfied; Q20a: 1=strongly agree, ..., 4=strongly disagree). If there are more than 2 missing responses then a total

Network

Protocol ESTEEM Statistical Analysis Plan

Variable	Type	Definition
		score is not calculated. To handle missing values, the final score is obtained by dividing the sum by the number of items answered. The outcome will then be computed as the difference in score at 12 months (and 3 and 6 months) and the score at baseline. If data at an assessment time point are missing, the outcome variable will be coded as missing. Scores should only be calculated for participants that are sexually active.
Change from Baseline Adaptation Index Hygiene subscale as 12 months	Continuous	The AI Hygiene subscale score will be computed at baseline and 12 months (and 3 and 6 months) using standard scoring algorithms. Specifically, instructions are to average the responses for questions Q1-Q4, Q9, and Q14 (0=never, 25=rarely, 50=sometimes, 75=often, 100=always). If there are at least 5 non-missing responses, then the score is the average of the non-missing responses, otherwise, the score is not calculated. The outcome will then be computed as the difference in score at 12 months (and 3 and 6 months) and the score at baseline.
Change from Baseline Fecal Incontinence Adaptation Index Avoidance subscale as 12 months	Continuous	The AI Hygiene subscale score will be computed at baseline and 12 months (and 3 and 6 months) using standard scoring algorithms. Specifically, instructions are to average the responses for questions Q5-Q8, Q10-Q13, and Q15-17 (0=never, 25=rarely, 50=sometimes, 75=often, 100=always). If there are at least 9 non-missing responses, then the score is the average of the non-missing responses, otherwise, the score is not calculated. The outcome will then be computed as the difference in score at 12 months (and 3 and 6 months) and the score at baseline.
Patient Global Impression of Improvement at 12 months	Dichotomous	For defining improvement, Yes="much better" or "very much better" on the PGI-I scale. The outcome will be computed at 12 months (and 3 and 6 months)
Patient Global Impression of Severity at 12 months	Categorical	For defining severity, Normal/mild="Normal" or "Mild" on the PGI-S scale. The outcome will be computed at 12 months (baseline, 3 months, and 6 months)

Network

Protocol ESTEEM Statistical Analysis Plan

Variable	Type	Definition
Change from Baseline Brink Score at 12 months	Continuous	The Brink Score will be calculated from the pelvic floor muscle assessment form. It is calculated by summing the Brink pressure, duration, and displacement metrics if the assessment could be performed (i.e. not unable to perform due to pain). The outcome will then be computed as the difference in Brink Score at 12 months (and 6 months) and the Brink Score at baseline. If data for the assessment time point are missing, the outcome variable will be coded as missing.
Change from Baseline Maximum Pelvic Floor Muscle Contraction Pressure (Maximum Amplitude) at 12 months	Continuous	The maximum amplitude from the Peritron device will be averaged across the valid squeeze measures (out of 3 possible). The outcome will then be computed as the difference in average maximum amplitude at 12 months (and 8 weeks) and the average maximum amplitude at baseline.

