4.5. Baseline Visit

At the baseline visit, the voiding diary will be reviewed to ensure that entries are clear and interpretable. If the first baseline voiding diary is not acceptable, the subject will be allowed one more attempt. If the second baseline voiding diary is not acceptable, the subject will not be eligible for the trial.

Once eligibility is confirmed, pre-treatment information will be obtained including:

- Demographics – age, race/ethnicity, education level
- Medical history – prior urinary incontinence procedures and treatments, prior pelvic surgeries, comorbidities, smoking, medications
- Physical exam – Body mass index, pelvic organ prolapse quantification (POPQ), PFM strength (Peritron and Brink measures)
- Questionnaires – self-administered

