Study population	-SUI or SUI predominant desiring non-surgical treatment	-Stage 2-4 prolapse with presence of SUI -All women underwent vaginal vault suspension -SUI defined as affirmative response to SUI item on UDI and objective confirmation	-No significant prolapse -No vaginal vault repair allowed - Bothersome mixed UI desiring midurethral sling (defined as at least moderate bother for both SUI and UUI items on UDI and confirmation on bladder diary)
Primary outcome definition	PGI-I and PFDI \leq somewhat bother for SUI items	UDI (urinary outcome) -Urinary outcome powered to detect 11 point diff in UDI	UDI(total)-long form -Powered to detect 35 point diff in UDI(total), 15 point in UDI(irrit), and 8 points UDI(stress) scales.
Primary outcome time point	3 months	-Urinary-short term 6 months for urinary sx -Prolapse-long term 2 years	12 months
# visits	4	5	6
Duration of active treatment	6 weeks	2 weeks preop to 3 months postop	2 weeks preop to 6 months postop
Interval between visits	Q2-3 weeks	Postop: (Q2-4 wks) 2, 4, 8 wks 3 months	Postop: 2, 4, 6, 8 weeks 6 months
Intervention components			
1. Bladder diary review	Yes	No	Yes
2. PFMT, technique eval	Yes	Yes	Yes
3. Standardized protocol for PFMT exercise progression	No	No	Yes
3. PFMT standardized "special circumstances"	No	No	Yes
3. SUI strategies	Yes	Yes	Yes
4. UUI strategies	Yes	Yes	Yes
5. Dysfx void strategies	No	Yes	Yes
6. Colorectal Sx strategies	No	Yes	No
7. Verbal/written home PFME Px	Yes	Yes	Yes
8. PFMT Adherence	Yes	Yes	Yes
9. Addressing other PFD Sx	No	Yes	No
10. Other written educational materials	SUI, UUI, PFME, Diary	SUI, UUI, PFME, Postop instructions, lifting, healthy bladder, healthy bowel	SUI, UUI, PFME, Diary

Control group			
	-Completed diaries same as intervention	-“Usual care” – routine periop teaching and standardized postop handouts -No diaries	-Will complete diaries at same time intervals as intervention group -Will have PFM measures same as intervention
Methods to standardize intervention			1. Interventionist checklist 2. Protocol for exercise progression 3. Interventionist protocol for “Special Circumstances” 4. Subject handouts that interventionist will review during education

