Change from baseline in UDI Obstructive Score at 12 months	Continuous	The Urogenital Distress Inventory-Obstructive Score will be computed at baseline and 12 months (and 3 and 6 months) using the standard scoring algorithm. Specifically, the instructions are to average responses across questions E, J, K, L, M, N, O, P, Q, R, and S and their respective sub-questions (0=No or Yes and Not at all; 1=Yes and Slightly; 2=Yes and Moderately; 3=Yes and Greatly), and then multiply by 100/3. If any responses are missing, then the score will be calculated as the average of the non-missing responses. The outcome will then be computed as the difference in score at 12 months (and 3 and 6 months) and the score at baseline. If data for an assessment time point are missing, the outcome variable will be coded as missing.
Exploratory Outcomes		
Change from baseline in Urge Incontinence Episodes at 12 months	Continuous	The daily frequency of urge incontinence episodes will be taken from the bladder diary. The outcome will then be computed as the difference in daily frequency of urge incontinence episodes at 12 months (and 6 months) and the daily frequency of urge incontinence episodes at baseline. If data for the assessment time point are missing, the outcome variable will be coded as missing.
Change from baseline in Stress Incontinence Episodes at 12 months	Continuous	The daily frequency of stress incontinence episodes will be taken from the bladder diary. The outcome will then be computed as the difference in daily frequency of stress incontinence episodes at 12 months (and 6 months) and the daily frequency of stress incontinence episodes at baseline. If data for the assessment time point are missing, the outcome variable will be coded as missing.
Change from baseline in Total Incontinence Episodes at 12 months	Continuous	The daily frequency of total incontinence episodes will be taken from the bladder diary. The outcome will then be computed as the difference in daily frequency of total incontinence episodes at 12 months (and 6 months) and the daily frequency of total

Network

Protocol ESTEEM Statistical Analysis Plan

Variable	Type	Definition
		incontinence episodes at baseline. If data for the assessment time point are missing, the outcome variable will be coded as missing.

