Change from baseline in Urgency Episodes at 12 months	Continuous	The daily frequency of urgency episodes will be taken from the bladder diary. The outcome will then be computed as the difference in daily frequency of urgency episodes at 12 months (and 6 months) and the daily frequency of urgency episodes at baseline. If data for the assessment time point are missing, the outcome variable will be coded as missing.
Change from baseline in Nocturia Episodes at 12 months	Continuous	The daily frequency of nighttime voids will be taken from the bladder diary. The outcome will then be computed as the difference in daily frequency of nighttime voids at 12 months (and 6 months) and the daily frequency of nighttime voids at baseline. If data for the assessment time point are missing, the outcome variable will be coded as missing.
Change from baseline in Daytime voids at 12 months	Continuous	The daily frequency of daytime voids will be taken from the bladder diary. The outcome will then be computed as the difference in daily frequency of daytime voids at 12 months (and 6 months) and the daily frequency of daytime voids at baseline. If data for the assessment time point are missing, the outcome variable will be coded as missing.
Change from baseline in total voids at 12 months	Continuous	The daily frequency of total voids will be taken from the bladder diary. The outcome will then be computed as the difference in daily frequency of total voids at 12 months (and 6 months) and the daily frequency of total voids at baseline. If data for the assessment time point are missing, the outcome variable will be coded as missing.
Change from baseline in total voids without incontinence at 12 months	Continuous	The number of voids without incontinence will be taken from the bladder diary. The outcome will then be computed as the difference in number of voids without incontinence at 12 months (and 6 months) and the number of voids without incontinence at baseline. If data for the assessment time point are missing, the outcome variable will be coded as missing.

Network

Protocol ESTEEM Statistical Analysis Plan

Variable	Type	Definition

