Change from baseline in Number of Pads per Day at 12 months	Continuous	The daily average number of pads will be taken from the bladder diary. The outcome will then be computed as the difference in daily average number of pads at 12 months (and 6 months) and the daily average number of pads at baseline. If data for the assessment time point are missing, the outcome variable will be coded as missing.
Change from baseline in Number of Wet Pads per Day at 12 months	Continuous	The daily average number of wet pads will be taken from the bladder diary. The outcome will then be computed as the difference in daily average number of wet pads at 12 months (and 6 months) and the daily average number of wet pads at baseline. If data for the assessment time point are missing, the outcome variable will be coded as missing.
Normalization of Voiding Frequency at 12 months	Dichotomous (Yes/No)	
The total number of daytime and nighttime voids will be taken from the bladder diary and summed and divided by the number of diary days (≤ 3) to get a voiding frequency. The indicator for normalization at 12 months (and 6 months) will be defined for each subject as follows:
 
If > 8 voids/24 hours at baseline: If > 8 voids/24 hours at time x: No If ≤ 8 voids/24 hours at time x: Yes
 
If ≤ 8 voids/24 hours at baseline: Missing
 
If data for the assessment time point are missing, the normalization indicator will be coded as missing.
 
The variable is summarized as the percentage of participants with indicator equal to “Yes” among all non-missing indicators.

Improvement in Voiding Frequency at 12 months	Dichotomous (Yes/No)	
The total number of daytime and nighttime voids will be taken from the bladder diary and summed and divided by the number of diary days (≤ 3) to get a voiding frequency. If there has been at least a 50% reduction in the voiding frequency between baseline and the time point, the improvement indicator at 12 months (and 6 months) will be set to “Yes”, otherwise it will be set to “No”. If data for the assessment time point are missing, the improvement indicator will be coded as missing.
 
The variable is summarized as the percentage of participants with indicator equal to “Yes” among all non-missing indicators.

Network

Protocol ESTEEM Statistical Analysis Plan

Variable	Type	Definition

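### SAP 9.2 defines the change in voids without incontinence from a diary count with no per-day division, so read literally it mixes voiding with diary length

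*SAP*

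**What the plan says.** In the SAP 9.2 table, the row for change from baseline in total voids without incontinence reads "The number of voids without incontinence will be taken from the bladder diary". The outcome is the "difference in number of voids without incontinence at 12 months (and 6 months) and the number of voids without incontinence at baseline". The row has no divisor and does not say per day.

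The neighbouring rows differ. For total voids: "The daily frequency of total voids will be taken from the bladder diary". For daytime voids: "The daily frequency of daytime voids will be taken from the bladder diary". For incontinence episodes: "The daily frequency of total incontinence episodes will be taken from the bladder diary". Urge and stress episodes, urgency episodes and night-time voids are also daily frequencies, and pads and wet pads are daily averages. That makes nine per-day rows and one that is not.

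The same table shows that diary length can vary. The voiding-frequency indicators take the summed voids "divided by the number of diary days (≤ 3) to get a voiding frequency", and the diary-dryness indicator also divides by diary days.

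Nothing elsewhere standardises this row. Its missing-data rule covers an absent assessment but not a partial diary. SAP 9.5.1 sends diary changes to the primary-outcome model, which has no term for diary days.

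**The concern.** A change in a count reflects a change in voiding only if both counts cover the same number of days. The SAP expects some diaries to run under 3 days and corrects for this in its dichotomous diary outcomes, but not here. Programmed as worded, the variable would record a difference in diary length as a difference in voiding, and in an individual woman it could reverse the sign of a true change. Even with complete diaries, this row would be a 3-day total beside a per-day row for total voids, of which it is a subset, with nothing in the definition to warn the reader.

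**Working it through.** The plan states no sample size, power or effect figure for this variable, so there is none to reproduce. The check is direct arithmetic on the definition.

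**Inputs.** From SAP 9.2: change = follow-up count − baseline count; diary days at most 3. Assumed, because neither document gives them: the rate m of voids without incontinence per day, and the share of short diaries.

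**Step 1: one woman, constant rate m.** Literal change = m × (follow-up days − baseline days).

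| Assumed m | 3 days, then 2 | 3 days, then 1 | 2 days, then 3 | Per-day change |
|---|---|---|---|---|
| 4 | −4 | −8 | +4 | 0 |
| 6 | −6 | −12 | +6 | 0 |
| 8 | −8 | −16 | +8 | 0 |
| 10 | −10 | −20 | +10 | 0 |
| Apparent change | −33% | −67% | +50% | 0% |

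The sign can reverse. A true rise from 6 to 8 per day, with a 3-day then a 2-day diary, gives 8 × 2 − 6 × 3 = 16 − 18 = −2. The per-day change is +2.

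**Step 2: added noise.** Assume a daily mean of 7, SD 2.5 (variance 6.25) and correlation 0.6 between visits (covariance 3.75), with 3-day baselines and short follow-ups unrelated to voiding. Let w = follow-up days / 3. Dividing the literal change by 3 puts it on the per-day scale:

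Variance = E[w²] × (6.25 + 49) − (7 × E[w])² + 6.25 − 2 × E[w] × 3.75

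The per-day change has variance 2 × 6.25 × (1 − 0.6) = 5.00.

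- 10% two-day: E[w] = 0.9667, E[w²] = 0.9444; variance 5.39, ratio 1.08.
- 10% two-day and 3% one-day: E[w] = 0.9467, E[w²] = 0.9178; variance 5.94, ratio 1.19.
- 20% two-day and 5% one-day: E[w] = 0.9000, E[w²] = 0.8444; variance 6.47, ratio 1.29.

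**Step 3: arm comparison with no true effect.** With 3-day baselines and two-day follow-up shares p in each arm, the false difference is m × (difference in p). Equal shares give 0. Hypothetical shares of 5% and 15% give 0.10 × m, or 0.4 to 1.0 voids for m = 4 to 10. That is on the 3-day count scale; divided by 3, it is 0.13 to 0.33 voids per day.

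**Step 4: all diaries complete.** At 7 voids a day without leakage, the row reads 7 × 3 = 21, beside a total-voids row in voids per day. Changes are three times too large for that scale, and there is no bias.

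**Step 5: after dividing each count by its own diary days.** The change is 0 for every combination in the table, and +2 for the rise from 6 to 8.

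**The case against.** The best defence is that this is a missing word. The row does not say raw, summed or 3-day total. The SAP also uses number loosely for variables it defines per day: sections 3.2.3 and 9.5.1 speak of the number of urge and urgency episodes, which section 9.2 defines as daily frequencies. With nine per-day rows around it, a programmer might well divide by days anyway. This is fair as a guess at intent, but section 9.2 is the specification, and for this row it omits the division.

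The consequence is also small. The variable is exploratory. It is named in no study aim, nor in the diary outcomes of protocol 3.4.3.a or the specific comparisons in SAP 9.5.1. This stands.

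A reader might infer two stronger things, and the documents support neither.

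- **Follow-up diaries are shorter than baseline diaries.** Protocol 4.5 says "If the second baseline voiding diary is not acceptable, the subject will not be eligible for the trial", and no matching rule exists for follow-up. But acceptable there means clear and interpretable entries; no minimum number of days is set. Baseline diaries could be short too, which pushes the error the other way.
- **Completeness differs by arm.** Table 10 in protocol 5.4 lists "1. Bladder diary review" as an intervention component. But protocol 5.3 and Table 10 have controls keep diaries at the same intervals, and Table 11 lists the diary for all subjects. Table 11 shows a BPTx visit at 6 months but none at 12 months, the time point in this row's title. An arm difference in diary length, and its direction, would be conjecture.

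**Conclusion.** Wrong as written, but minor. The stated rule gives a wrong value whenever a woman's diary lengths differ between visits, and nothing else in either document corrects it. For one woman with a 2-day diary after a 3-day one, the error is −4 to −10 voids at an assumed 4 to 10 per day. Across the trial, the supportable effect is extra noise: about 8% to 29% more variance under the assumed rate, SD, correlation and short-diary shares of 10% to 25%. The documents do not report how many diaries are short, so the real figure cannot be computed from them.

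A systematic false fall in voids, or a false arm difference, should not be claimed. Each needs an imbalance in diary length, between visits or between arms, that the documents do not show. If all diaries cover 3 days, only the threefold scale mismatch remains. The primary and secondary UDI analyses are untouched.

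**What to change.** In this row of SAP 9.2, define the variable as voids without incontinence divided by the number of diary days at that visit, and take the difference from baseline afterwards. Then confirm that the analysis program does this. If it already does, only the wording changes.

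The cost is one phrase in the SAP and at most one line of code. No new data are needed, since diary days are already used for the voiding-frequency and dryness indicators.
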